### 5.3 Response assessment and classification

Only patients with measurable disease at baseline should be included because objective tumor response is a part of the primary endpoint. Tumor assessments will be taken at baseline and during a defined window at the end of each *Block* and at 1 year.

#### 5.3.1 Measurable lesions

Measurable Lesions are lesions that can be accurately measured in two perpendicular diameters, with at least one diameter  $\geq 20$  mm and the other dimension  $\geq 10$  mm (10 mm x 10 mm for spiral CT). The area will be defined as the product of the largest diameter with its perpendicular

#### 5.3.2 Non-measurable lesions

All other lesions, including unidimensionally measurable disease and small lesions (lesions without at least one diameter  $\geq 20$  mm), and any of the following:

- Lesions occurring in a previously irradiated area (unless they are documented as new lesions since the completion of radiation therapy), bone lesions, leptomeningeal disease, ascites, pleural or pericardial effusion, lymphangitis cutis/pulmonis, abdominal masses that are not pathologically/cytologically confirmed and followed by imaging techniques and cystic lesions.

All measurable and non-measurable lesions should be measured at screening and at the defined tumor assessment time points. Extra assessments may be performed, as clinically indicated, if there is a suspicion of progression

#### 5.3.3 Immune-related response criteria (irRC)

The irRC are the measurement of overall tumor burden as a metric of disease progression, as compared to the limitation to baseline lesion measurements taken with WHO and RECIST. According to irRC, new lesions do not constitute disease progression if net tumor burden (including new lesions) is stable or decreases. The irRC also permit disease progression prior to response and introduce the concept of confirmation of progression at a subsequent time point after first detection. This accounts for the period required for activated T-cells to infiltrate the tumor, which may cause initial tumor volume increase but can subsequently translate into tumor shrinkage. The irRC also classify durable stable disease as clinical activity. (Wolchok et al., 2009)

Note: irRECIST will be used for the primary response tabulations.

### 5.3.4 Overall Response According to Immune-related response criteria (irRC)

FIGURE 5: *irRC SUMMARY*

|                                                      | irRC                                                                                                                                        |
|------------------------------------------------------|---------------------------------------------------------------------------------------------------------------------------------------------|
| New, measurable lesions (i.e. $\geq 5 \times 5$ mm)  | Incorporated into tumor burden                                                                                                              |
| New, nonmeasurable lesions (i.e., $< 5 \times 5$ mm) | Do not define progression (but preclude irCR)                                                                                               |
| Non-index lesions                                    | Contribute to defining irCR (complete disappearance required)                                                                               |
| Complete Response (CR)                               | Disappearance of all lesions in two consecutive observation not less than 4 weeks apart                                                     |
| Partial Response (PR)                                | $\geq 50\%$ decrease in tumor burden compared with baseline in two observations at least 4 weeks apart                                      |
| Stable Disease (SD)                                  | 50% decrease in tumor burden compared with baseline cannot be established nor 25% increase compared with nadir                              |
| Progressive Disease (PD)                             | At least 25% increase in tumor burden compared with nadir (at any single time point) in two consecutive observations at least 4 weeks apart |
| Near Complete Response (Near CR)                     | Reduction in tumor by $> 90\%$ and no new lesions in two consecutive observations not less than 4 weeks apart.                              |
| Unknown (UN):                                        | Assessment of target lesions cannot be made due to insufficient or unevaluable data. In this case, a concise explanation must be given.     |

Note: If tumor response data is missing for target lesions, the overall assessment must be UN (unknown) unless there is new disease that would result in an overall assessment of PD. However, if there is missing or unevaluable data for non-target lesions, but data is available for all target lesions, the overall response for that time point will be assigned based on the sum LD of all target lesions. Additionally, the assessment of CR cannot be made if there is missing or unevaluable data for non-target lesions. In this case, the overall assessment would be PR.

Definition of New Lesion: Previously unseen lesions  $> 5 \times 5$  mm in size will be incorporated into tumor burden.

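### The missing-target Note in Section 5.3.4 is incomplete: measured growth already past the progression cut-off must be scored unknown, and the new-disease exception has no stated test

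*Combined protocol and SAP*

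**What the plan says.** The Note under Figure 5 in Section 5.3.4 opens with the condition "If tumor response data is missing for target lesions" and then rules that "the overall assessment must be UN (unknown) unless there is new disease that would result in an overall assessment of PD". It does not say whether one missing target lesion is enough. Its next sentence deals with scans on which every target lesion is available, so the natural reading is that any missing target triggers the rule.

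The surrounding text defines the labels as follows:

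- Progression (Figure 5): "At least 25% increase in tumor burden compared with nadir (at any single time point) in two consecutive observations at least 4 weeks apart".
- New measurable lesions (Figure 5): "Incorporated into tumor burden". New non-measurable lesions cannot define progression.
- New lesions in general (Section 5.3.3): "new lesions do not constitute disease progression if net tumor burden (including new lesions) is stable or decreases".
- Unknown (Figure 5): "Assessment of target lesions cannot be made due to insufficient or unevaluable data".

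The label has two uses. PFS in Section 8.4 runs to the first progression or death. Section 5.9 lists confirmed radiographic progression among the reasons for discontinuation.

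**The concern.** Two things are wrong with the rule as written.

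First, the only way out of an unknown score is new disease. There is no provision for a scan on which the target lesions that were measured already put the burden past the progression cut-off. Such a scan can be assessed, because no value of the missing lesion changes the answer. The Note still requires it to be unknown, which fits poorly with Figure 5, where unknown is kept for assessments that cannot be made.

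Second, under Sections 5.3.3 and 5.3.4 new disease counts through total burden. With target lesions missing, that total cannot be formed, and the Note does not say how an assessor decides that new disease leads to progression. One assessor could call progression on a small new lesion while another records unknown for the same scan.

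At stake are the date of progression in the PFS analysis and the consistency of the label that feeds the confirmed-progression criterion.

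**Working it through.** The plan gives no figure to reproduce here, so the check is on the logic of the rule.

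**Inputs.** The cut-off is 1.25 x nadir burden (Figure 5). Lesion area is the product of two perpendicular diameters (Section 5.3.1). New measurable lesions are added to burden (Figure 5). The lesion sizes below are illustrative assumptions. The nadir is assumed to come from a scan with all targets measured and is set at 1000 mm², so the cut-off is 1.25 x 1000 = 1250 mm².

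**Formula.** A missing lesion has an area of zero or more, so

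burden ratio ≥ (measured target area + measurable new lesion area) / nadir burden.

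If the right-hand side is at least 1.25, the cut-off is met whatever the missing lesion measures.

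**Cases.**

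1. Nadir lesions of 400, 300 and 300 mm². Two are now 900 and 700 mm², the third is not assessed, and there is no new disease. (900 + 700) / 1000 = 1.60. The cut-off is certainly met. The Note requires unknown.
2. Measured targets 1300 mm², one target missing, no new disease. 1300 / 1000 = 1.30. The cut-off is certainly met. The Note requires unknown.
3. Measured targets 400 mm², one target missing, one new 6 x 6 mm lesion (36 mm²). 436 / 1000 = 0.436. The missing lesion would have to be at least 1250 - 436 = 814 mm² to reach the cut-off. Progression cannot be shown.
4. All targets missing, one new 6 x 6 mm lesion. 36 / 1000 = 0.036. The missing lesions would have to total at least 1250 - 36 = 1214 mm². Progression cannot be shown.
5. All targets missing, one new 40 x 35 mm lesion (1400 mm²). 1400 / 1000 = 1.40. The cut-off is certainly met, by new disease alone.

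For comparison, if the targets are unchanged from nadir, a new lesion needs 250 mm² to reach the cut-off, which is a square of about 15.8 mm (√250).

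**Timing, scheduled imaging only.** Section 7.1.2.6 puts scans about 9 to 12 weeks apart during treatment. If the scan forced to unknown would have been the first to show progression, the progression date moves by one interval, 9 to 12 weeks. If it would have been the confirming scan, the result depends on whether an unknown scan interrupts two consecutive observations, which the documents do not say. If it does not interrupt, the date stands and confirmation comes one interval later. If it does, the first date is lost and the next possible one is two intervals later: 2 x 9 = 18 to 2 x 12 = 24 weeks.

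**How many scans.** Section 5.3 gives five post-baseline assessments (four block ends and 1 year). For 24 evaluable patients this is at most 24 x 5 = 120 scans, fewer once patients stop. The documents give no missing-target rate. An assumed 5 to 10% would give 6 to 12 scans under the rule. That counts every scan with a missing target. The number mislabelled is smaller and could be zero.

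**Metric.** The Note's sentence on missing non-target data says "the overall response for that time point will be assigned based on the sum LD of all target lesions". That is a sum of diameters, while Section 5.3.1 uses area and Section 5.3.3 names irRECIST for the primary tabulations without defining it. The lower-bound argument holds for either measure, since a missing diameter is also zero or more, but the mm² figures apply only to area.

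**The case against.** A reader might infer that the exception is the wrong way round: that the Note lets any new lesion give progression, which the immune-related criteria reject. The documents do not support that. The exception is limited to new disease that would lead to an overall assessment of progression, and this can be read as new disease that meets the burden rule. Section 5.3.3 rules out progression from new lesions only when net burden is stable or falls, and Figure 5 rules it out for non-measurable lesions. Case 5 shows that a large new measurable lesion can reach the cut-off alone, so the exception is sometimes right. It would equally be wrong to replace it with a statement that new disease alone never gives progression.

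A reader might also infer large delays and false progressions. Section 5.3.2 allows extra scans when progression is suspected, so a wait of 9 to 12 weeks is not forced. Figure 5 requires two observations, and Section 5.9 refers to confirmed progression with a possible exception for clinically stable or improved patients. One incomplete scan with a tiny new lesion therefore settles neither. The 18 to 24 weeks depends on a reading of consecutive that the documents do not state.

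Finally, the primary endpoint is ORR. Neither unknown nor progression is a response at that visit. PFS is estimated by Kaplan-Meier without a planned test, and Section 4.4.4.1 says it does not lend itself to definitive analysis here.

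All of this limits the size of the problem. It does not remove cases 1 and 2, where the Note's plain wording gives a label that the measurements contradict, or the missing test in cases 3 and 4.

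**Conclusion.** The Note is incomplete and partly ambiguous, and should be corrected. It requires an unknown score for scans on which measured target growth alone already passes the 25% cut-off. It also leaves undefined how new disease leads to progression when total burden cannot be formed, so a small new lesion could be labelled progression against Sections 5.3.3 and 5.3.4.

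The effect is confined to PFS dating and the label of confirmed progression, in a small number of scans that cannot be estimated from the documents. There is no direct effect on ORR. The conclusion assumes that one missing target lesion is enough to trigger the rule. If the rule were meant only for scans with every target missing, the partly measured scan would have no rule at all and the Note would still need the same clarification.

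**What to change.** Replace the sentence in the Note with:

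> If any target lesion is not assessed, the time point meets the PD cut-off if the measured target lesions plus measurable new lesions already total at least 1.25 x nadir burden; otherwise it is UN. New lesions count only through their measured size. The usual confirmation applies, and a UN time point does not break a consecutive pair.

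This gives progression (subject to confirmation) in cases 1, 2 and 5, and unknown in cases 3 and 4.

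In the same edit, settle which measure applies. The sum of longest diameters in the Note, the area in Section 5.3.1 and the irRECIST statement in Section 5.3.3 need to be reconciled. If the chosen criteria carry a different progression cut-off, the replacement sentence should use that one.

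The cost is one replaced sentence and a decision on the measure, with no new scans or data. The discontinuation criteria in Section 5.9 are left as they are. The downside is that a few scans may be reclassified, some to earlier progression and some from progression to unknown.

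### When non-target data are missing, section 5.3.4 assigns response on a diameter sum of target lesions, for which the plan prints no cut-off and which, read literally, omits new lesions

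*Combined protocol and SAP*

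**What the plan says.** Five places in the combined protocol and SAP bear on this.

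- **Unit of measurement, section 5.3.1.** Lesions are measured in two perpendicular diameters: "The area will be defined as the product of the largest diameter with its perpendicular".
- **Cut-offs, section 5.3.4, Figure 5.** PR is a fall of at least 50%, worded as a "decrease in tumor burden compared with baseline in two observations at least 4 weeks apart". PD is "At least 25% increase in tumor burden compared with nadir", seen at two consecutive observations. New measurable lesions are added to the burden. Non-index lesions enter only the definition of CR.
- **Missing-data rule, section 5.3.4, Note under Figure 5.** The rule applies "if there is missing or unevaluable data for non-target lesions, but data is available for all target lesions". In that case "the overall response for that time point will be assigned based on the sum LD of all target lesions". The Note adds that "the assessment of CR cannot be made if there is missing or unevaluable data for non-target lesions", and such a case is called PR. If target data are missing, the result is unknown unless new disease makes it PD.
- **New lesions, section 5.3.4, after the Note.** Previously unseen lesions above 5x5 mm "in size will be incorporated into tumor burden".
- **Criterion for the primary tabulation, section 5.3.3.** irRECIST is named, but the documents print neither its measure nor its cut-offs. RECIST 1.1 is cited in the eligibility criteria, for measurable disease at entry.

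LD is not spelled out in the Note; I read it as longest diameter. I also take target and index lesions to be the same thing, and likewise non-target and non-index.

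**The concern.** The Note names a measure that matches the printed criteria in neither dimension nor scope. It has one diameter where section 5.3.1 has two. It counts target lesions only, where Figure 5 counts target plus measurable new lesions. It also brings no cut-off of its own, so an assessor must either carry over the 50% and 25% from Figure 5 or import a figure from outside the plan.

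Nothing in Figure 5 calls for the change. Non-target lesions matter there only for CR, and the Note already bars CR in this situation. ORR counts CR and PR alike, so that bar does not itself move the primary endpoint. The diameter sum can.

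The efficacy decision in section 8.4 is sensitive to single patients: 3 versus 4 responders of 15 at stage 1, and 7 versus 8 of 24 at the end (29.2% versus 33.3%). A responder call could depend on whether a non-target lesion happened to be readable on a given scan. The PD call, and with it PFS, is exposed in the same way.

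**Working it through.** **1. The plan's own design figures.** Inputs from section 8.4: null rate 0.20, alternative 0.45, stop at 3 or fewer of 15, reject the regimen at 7 or fewer of 24.

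- Early termination at 0.20: P(X ≤ 3 | 15, 0.20) = 0.648 (plan: 0.65).
- Expected sample size: 15 + (1 − 0.648) × 9 = 18.17 (plan: 18).
- Exact type I error is 0.0835 and exact power is 0.9001 (plan: 10% and 90%).
- A full search gives this same design as the minimax one.

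The design reproduces and is not in question.

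**2. Area against diameter, uniform change.** If every diameter changes by a fraction d, area changes by (1 + d)² − 1.

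| Diameter change | Area change |
|---|---|
| −29.3% | −50% |
| −30% | −51% |
| −50% | −75% |
| +11.8% | +25% |
| +25% | +56.3% |

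If the printed cut-offs are carried over to diameters, a diameter fall from 29.3% to just under 50% is PR by area and not by diameter. A rise from 11.8% to just under 25% meets the PD threshold by area and not by diameter. Outside those bands, and with no new lesion, the two measures agree. If a 30% diameter cut-off is assumed instead (not printed in the plan), the PR band shrinks to area falls between 50% and 51%.

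**3. Example without a new lesion (assumed sizes).** A 40x30 mm target becomes 27x20 mm.

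- Area: 1200 to 540 mm², 540/1200 − 1 = −55%. PR by Figure 5.
- Diameter: 40 to 27 mm, 27/40 − 1 = −32.5%. Not PR at 50%; PR at an assumed 30%.

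**4. Example with a new lesion (assumed sizes).** A 40x30 mm target becomes 19x14 mm and a new 30x25 mm lesion appears.

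- Area burden with the new lesion: 266 + 750 = 1016 mm², 1016/1200 − 1 = −15.3%. Not PR.
- Diameter burden with the new lesion: 19 + 30 = 49 mm, 49/40 − 1 = +22.5%. Not PR at any cut-off.
- Target-only diameter: 19/40 − 1 = −52.5%. PR at 50% and at 30%.

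This discordance comes from leaving out the new lesion. It remains whichever measure is chosen.

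**5. Illustrative effect on power.** Suppose a share m of true responders is permanently lost, so the effective rate is 0.45 × (1 − m). The shares are assumptions; the documents give no rate of missing non-target data.

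| m | Effective rate | Exact power |
|---|---|---|
| 0 | 0.45 | 90.0% |
| 5% | 0.4275 | 85.7% |
| 10% | 0.405 | 80.3% |

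Wrongly counting a patient as in step 4 would push ORR the other way. That is not included here.

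**The case against.** The strongest reply is that irRECIST is the named criterion for the primary tabulations. If the sponsor means a diameter-based criterion, the diameter sum is the primary measure and nothing switches between scans. With a diameter cut-off near 30%, the shrinkage discordance almost vanishes. This stands as far as it goes: the documents do not settle whether area or diameter is the base measure, and Figure 5 itself states no unit. It does not rescue the clause, because a target-only sum still departs from section 5.3.3, which counts new lesions in net burden (step 4).

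A second reply is that the new-lesion sentence right after the Note makes no exception for these scans, so new lesions may still count. That reading is fair. But the Note names only target lesions, and two careful assessors could read it differently.

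A third concerns reach, and it also stands. The rule needs complete target data and at least one non-target lesion. Section 7.1.2.6 asks that imaging cover all known disease sites. PR needs two observations that Figure 5 does not require to be consecutive, and section 5.3 schedules assessments after each of four blocks and at 1 year. One affected scan need not cost a responder.

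A reader might infer more: that every patient with missing non-target data is misclassified, that about half of area-based responders would be lost at such scans, or that the trial loses 4 to 10 points of power. The documents do not support these. They would require the 50% and 25% cut-offs to be applied to diameters, which the Note does not say, together with a missingness rate that appears nowhere and losses that no later scan repairs.

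**Conclusion.** The point holds in limited form. For scans with complete target data but missing or unevaluable non-target data, the plan states a response rule that does not fit its own printed criteria and lacks a cut-off. The same patient can be scored differently at such a scan; many would not be.

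The shrinkage part depends on the cut-off applied: it is material if the printed 50% is used on diameters and close to nil if 30% is assumed. The new-lesion part does not depend on area versus diameter, but it does depend on reading the Note literally. That the printed burden is area-based is an inference from section 5.3.1 read with Figure 5.

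Frequency is unknown, so the power figures show sensitivity and do not estimate a loss. The rule still deserves correction because it feeds the primary endpoint, where one patient can decide the result.

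**What to change.** Restate the clause so that, when non-target data are missing or unevaluable and target data are complete, response at that time point is assigned from the same tumor burden measure and cut-offs used at all other time points for the primary tabulation: target lesions plus measurable new lesions, with CR not assignable.

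This depends on one decision by the sponsor: state in section 5.3 what irRECIST means here, whether burden is a sum of areas or of diameters, and which PR and PD cut-offs go with it. The diameter wording in the Note should then be kept or replaced to match. Deleting it first would presume that area is the primary measure.

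The cost is one sentence in section 5.3.4 plus a short definition of the primary measure. No new data are needed, since section 5.3.1 already calls for both diameters and section 5.3.2 for measuring lesions at each assessment. The change should be made before responses are adjudicated. The sample size and the two-stage rule do not change.

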### 5.4 Randomization or Treatment Allocation

There is no randomization on this trial.

### 5.5 Stratification

There is no stratification on this trial, as there is only one arm..

Risk features are tabulated for accommodation of retrospective comparisons of outcomes.

These may include:

1. Age
2. Time from diagnosis to treatment
3. Sites of metastatic disease
4. Absolute neutrophil count
5. Hemoglobin
6. Platelet count
7. LDH
8. Calcium
9. Albumin
10. Nephrectomy status
11. Prior therapy

## **5.6 Concomitant Medications/Vaccinations (allowed & prohibited)**

Medications or vaccinations specifically prohibited in the exclusion criteria are not allowed during the ongoing trial. If there is a clinical indication for one of these or other medications or vaccinations specifically prohibited during the trial, discontinuation from trial therapy or vaccination may be required. The investigator should discuss any questions regarding this with the Merck Clinical team. The final decision on any supportive therapy or vaccination rests with the investigator and/or the subject's primary physician.

